mM	millimoles
mmHg	Millimeters of mercury
Na ₂ HPO ₄	sodium phosphate
NaCl	sodium chloride

PAC-QOL	Quality of Life Questionnaire for the evaluation of the patient With constipation
PCR	Polymerase chain reaction
RNAr	Ribosomal ribonucleic acid
SF36	Quality of life questionnaire
SII	Irritable Bowel Syndrome
SmartPill ©	Wireless Motility Capsule
BP	Blood Pressure
CFU / g	Colony Forming Units per gram

6. Theoretical framework
 Explain in detail the foundations available to date in Which the Proposed study (biological sense, data About animals or in experiments in humans):
 a) background
 b) problem definition
 c) justification

1. Theoretical framework (It is completely Reorganized)

constipation

Introduction

Constipation is one of the gastrointestinal disorders MOST frequent That Affects around 20% of the western population, being more frequent in the female gender (M1.5: H1). Constipation can be primary, When causes constipation associated With (medication, mechanical obstruction, spinal cord injury, etc.) and secondary, When other factors Have Been diagnosed, more Frequently in population With onset or worsening of constipation after the 50 years of age¹. Functional constipation defined by the ROME III criteria requires the presence of symptoms 3 days in a month for 3 months, continuous or discontinuous, Whose symptom onset has-been in the last 6 months: 1) Increase in pushing, 3) hard stool, 3) feeling of obstruction / blockage During evacuation, 4) use of digital maneuvers,

Besides age and genre, other risk factors are associated With constipation: race, physical inactivity, low socio-economical level, chronic use of medication, low intake of fiber and water and psychological comorbidity (eating disorders, depression, etc.). ¹

Treatments

There are multiple therapeutic options for the management of constipation, changes in lifestyle Including, the intake of fiber, laxatives and pharmacological treatment and in selected cases (colonic inertia) surgery. The first option in the therapeutic management for Patients With constipation are changes in lifestyle, Among Which is the type of diet (increase in fiber intake, Which Has Been Associated With an improvement in the fecal matter and the evacuation frequency), liquid intake and exercise⁵ .

The dietary fiber has a role in the Very Important gastrointestinal tract, esta happens With any non-digestible carbohydrate (CH) That gets to the color, ferments intestinal bacteria Where it partially or completely, for short chain fatty acids (SCFA) and gases. Dietary fibers can be associated gastrointestinal symptoms With, mainly flatulence, abdominal distention and pain, as well as meteorism, due to the anaerobic bacteria in the fermentation of fiber colon⁶.

Many types of fiber Have Been Used, Plantago Psyllium being The One with more scientific evidence backing it up, starting at dose of 10g per day, at Least for 4 Weeks with an average response of 57%. Plantago psyllium is a long chain Considered moderately fermentable CH; it is a type of mucilage That Provides viscosity to stool through formation of gels I related to a peristaltic action in the intestine and Causing Increase in the intestinal motility. It is one of the agents of fecal matter forming Most Used for constipation control⁷⁻⁸. Among the contraindications for ITS use are: intestinal obstruction and sub-occlusion, abdominal pain, nausea, hypersensitivity, flatulence, abdominal distension and severe meteorism⁹. ACCORDING to the American Gastroenterological Association Medical Position Statement on Constipation (AGA) They recommend Plantago Psyllium With a supplementation of 15g / day in Patients With Functional constipation¹⁰.

The genre, Agave Tequilana Webber var. Blue stands out as an agronomically and economically crop in Mexico Important Which has relevance in the national and the international market, Besides its usefulness in the sugar and soluble dietary fibers, for ITS prebiotic fructans and Its beneficial effect ability in health. About 60-85% of the carbohydrates in agave are fructans and the type of link β (2-1) presents it causes the salivary, gastric and enteric enzymes not to be hydrolyzed by humans, Which causes them to arrive intact to the intestine and can be subject to fermentation by the colon microbiota, especially bifidobacterial by. It Has Been Reported That Can Regulate the intake ITS lipid metabolism through the synthesis of triglycerides, and thanks to it soluble fiber percentage, beneficial effect It provides on the gastrointestinal physiology,

Thanks to its branched structure That Confers ITS prebiotic effect at the same time it is classified That as soluble fiber, Which is fermented in the colon by bacteria endogenous, giving rise to metabolic and energetic substrates. Due to ITS osmotic potential and Its excessive fermentation, some secondary effects Caused by ITS Intakes are flatulence, meteorism, abdominal pain and discomfort, as well as diarrhea^{17,18}.

It has-been associated in vitro and in vivo preliminary studies, with the Increase bifidobacteria and lactobacillus of the population When They are Compared with a placebo. In the same way, there is a trend of

Presenting an improvement in the consistency of evacuations, as well as a decrease in the feeling^{19,20} constipation.

It has-been associated in vitro and in vivo preliminary studies, with the Increase bifidobacteria and lactobacillus of the population When They are Compared with a placebo. In the same way, there is a trend of presenting an improvement in the consistency of evacuations, as well as a decrease in the feeling^{21,22} constipation.

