The study to be Carried out will be Explained and read and, where appropriate, the informed consent will be signed by the Patient During the initial visit (Visit 1) of eligibility, Where the subject will be Given 2 questionnaires (see annexes), one They meet to determine if the ROME III criteria for functional constipation (FC) and another to ASSESS if the patient does not meet the criteria for irritable ROME III bowel syndrome (IBS) and a baseline breath test will be performed.

Having met the inclusion criteria, the patient will be EVALUATED by a graduate in nutrition with the objective of Evaluating the fiber intake in the subject's usual diet. The amount of daily fiber intake will be standardized and a diary will be Given to Evaluate Said intake (see annexes) as well as a diary Where the subject will keep a record of his / her evacuations (see annexes).

In Addition, the previous use of fiber supplements and laxatives, which must be suspended at Least 2 months prior to randomization, will be EVALUATED.

The subject will return to a second visit (Visit 2) (Which will depend on Whether the patient is taking laxatives or fiber supplements) for a complete physical evaluation and the fiber intake diary will be Assessed to determine the amount of fiber intake in the diet as well as the diary of evacuations and the SmartPill © will be Given and That way, the patient will return to the hospital to register the data after the capsule Having evacuated.

The patient will return a week later (Visit 3) on a 12 hour fast, the fiber intake and the evacuation diaries will be re-EVALUATED and will be EVALUATED They again by a nutritionist. A new breath test will be Carried out. The subject will be

Asked to complete the SF-36 Quality of Life Questionnaire. A stool sample will be Collected for ITS analysis in Addition to a blood sample for determination of fasting glucose, glycosylated hemoglobin A1c, Insulin and full lipid profile.

The subjects will be randomized to receive one of four treatments That can be Psyllium plantago 15g, blue agave Tequilana Weber fructans at doses of 5, 10g and blue agave Tequilana Weber fructans at a dose of 5 g + 10 g excipient for a concentration of 33 % of blue agave fructans Tequilana Weber.

The randomization will be computer-generated with a participation number and the assignment of the treatment will be consecutive.

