The product will be supplied in identical bottles With the same amount of powder in a container That will only be identifiable With the name of the protocol as well as the patient's number.

The patient will be provided with a measuring spoon to administer the amount of product Necessary for each of the doses (5, 10 and 15g respectively) or with envelopes Containing the exact Amounts Weighed.

The patient will be instructed to keep a diary of the diet, of the evacuations and a sheet to ASSESS adverse effects. The subject will return (Visit 4) at the end of a month \pm 5 days on a 12 hour fast and Their adherence will be Assessed by product weight in the container subtracting the number of grams required daily ACCORDING TO the assignment of treatment.

The fiber intake diaries will be EVALUATED again by the nutritionist, the evacuation will Also be EVALUATED diary. A medical evaluation will be Carried out That includes questioning and physical evaluation. Subsequently, a blood sample will be to determine fasting glucose Obtained, glycosylated hemoglobin A1c, insulin and lipid profile and a full sample of excrement will be Obtained and SmartPill® will be Given.

The patient will Continue with the supplement in the same container and will be scheduled for a month later. In the end-of-treatment visit visit (visit 5), the fiber will be EVALUATED journals consumption again by a nutritionist and the evacuation will be EVALUATED diary as well.

A medical evaluation will be Carried out That includes questioning and physical evaluation and Their adherence will be Assessed by weighing the product in the container, subtracting the number of grams That it requires daily ACCORDING to the treatment assignment or delivery by the patient of the empty envelopes used.

Subsequently, a blood sample will be to determine fasting glucose Obtained, glycosylated hemoglobin A1c, insulin and lipid profile and a full sample will be Collected stool and breath test at the end will be Carried out.

For end of the visit, Which Will Be Carried out one month after stopping the treatment, the evacuation will be EVALUATED diary and a stool sample will be Collected and with it the intervention in the part of the study will end. Total The follow-up duration for each patient will be 3 months, enough time to observe and compare the effect of the fibers to be used. It is Important to mention That in recent studies Carried out by the same team and with blue agave Tequilana Weber fructans,

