- functional constipation ROME III criteria as
- Subjects ≥55 years with recent colonoscopy (<3 years)

b) Exclusion criteria

- Taking supplements of fiber in the last 2 months
- Stimulant laxatives consumption chronically (Senna, Bisacodyl)
- decompensated comorbidities (example: uncontrolled diabetes mellitus HbA1c > 9%, decompensated Organ failure, decompensated hypertension (untreated or TA > 160 mmHg systolic and 95 mmHg diastolic)

- Using digital maneuvers or enemas to achieve evacuation
- Personal history of active or previous cancer
- abdominal surgery (except appendectomy, cholecystectomy, hysterectomy)
- Presence of alarm data in the last 6 months (trans-rectal bleeding, unexplained weight loss, abdominal pain)
- Use of drugs known promote constipation (opioid derivatives, clacioantagonistas, anticholinergics tricyclic antidepressants type)
- Prostration (immobility or poor mobility)
- Diseases such as untreated hypothyroidism with hormone replacement, and diseases associated with hypercalcemia that promote constipation
- Other causes of secondary constipation
- Meet criteria for constipation predominant irritable bowel
- Pregnancy.

c) Elimination criteria (considering pregnancy if necessary).

- Requiring individuals to withdraw their informed consent
- acute illness (eg appendicitis, medical-surgical requiring hospitalization intervention and follow-up)
- In our study provides no substitute for patients who have completed or prematurely abandoned the study. It is contemplated an analysis by intention to treat and the percentage of losses for each treatment group will be collected, clarifying the reason why the study was abandoned.

10. Methodology: Outcomes and variables

a) Variables / Main outcome measure

b) Variables / secondary endpoints measured

b) frequency measurements,

c) Criteria for success and failure, and if necessary

d) Strategy statistical analysis.

Where applicable should be specified and substantiated techniques, equipment and / or instruments to be used in the measurement (this includes mechanical / electronic / cyber special equipment, evaluation forms, questionnaires, matching tables, etc.), indicating the validity criteria , reproducibility and quality controls that are the same.

main outcome variable:

Effect of supplementation of fructans Tequilana Weber blue agave in increasing at least one complete evacuation from basal spontaneous.

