Discomforts generated by the study:

Discomfort from the study are related to the puncture for blood collection (3). It is anticipated that the fiber, when containing fructans, generate a fermentation process with flatulence and bloating. However, reports of studies using the fiber, have shown that this effect is transient lasting 2 weeks.

Risks:

Regulation of the General Law of Health in Research for Health, said that obtaining biological samples represents a minimal risk in the investigation. The risks of blood sampling are: possibility of slight bleeding or bruising at the puncture site, dizziness or fainting and rarely arterial puncture may occur. Personnel draw the blood sample is trained for this, which will minimize the risks of complications.

If there are complications will be referred directly to your treating physician. It is anticipated in the informed consent we do not have resources in case complications arise.

Benefits:

Administration fiber, it has shown to be healthy and beneficial for the treatment of functional constipation. Such supplementation, is the first line treatment of functional constipation. Patients entering this study will benefit from fiber start treatment within the diagnostic and therapeutic approach constipation.

Moreover, thanks to the participation of volunteers, your community can benefit significantly by finding new ways to address this medical complication.

Rescue measures:

If the patient has no spontaneous evacuation after 72h will prompt the patient to contact the research team, for instructions such as laxatives previously prescribed by your physician. If distended or flatulence, using anti detergents (simethicone) that is effective to treat this condition is allowed. For present colic, it can be used a conventional antispasmodic. each of the side effects will be recorded as well as the need for therapies rescues specified above.

13. Schedule of activities

The letter updating the research project is attached. (Annex 1)

Activities	2018												2019												2020											
	J	F	M	A	M	J	J	A	S	O	N	D	J	F	M	A	M	J	J	A	S	O	N	D	J	F	M	A	M	J	J	A	S	O	N	D
Moith																																				
Research topic selection	■																																			
Search and review of the biography	■	■	■	■	■	■	■	■	■	■	■	■	■	■	■	■	■	■	■	■	■	■	■													
Protocol writing	■	■																																		
Review of the protocol by the research group			■	■																																

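### No selection criterion excludes known hypersensitivity to a study product, although the protocol lists it as a contraindication to psyllium, the comparator given to 15 of 60 patients

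*Combined protocol and SAP*

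**What the plan says.** **Contraindications.** Section 6, Treatments, describes psyllium and states: "Among the contraindications for ITS use are: intestinal obstruction and sub-occlusion, abdominal pain, nausea, hypersensitivity, flatulence, abdominal distension and severe meteorism".

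**Exposure.** Section 8 randomises 60 patients to four groups of 15: agave fructans 5 g, agave fructans 10 g, agave fructans 5 g with 10 g of excipient, and psyllium 15 g. The study is single blind. The product comes in identical bottles that carry only the protocol name and the patient number.

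**Entry.** Section 8 gives the Rome III items and says that an evaluation will be made of "the previous use of fiber supplements and laxatives, which must be suspended at Least 2 months prior to randomization". Section 9 gives the inclusion and exclusion criteria. The only exclusion that concerns fiber products reads "Taking supplements of fiber in the last 2 months".

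**On treatment.** Section 8 provides an adverse-effect sheet and medical evaluations at visits 4 and 5. After visit 4, "The patient will Continue with the supplement in the same container and will be scheduled for a month later". Section 9 c) eliminates patients who withdraw consent and those with "acute illness (eg appendicitis, medical-surgical requiring hospitalization intervention and follow-up", and adds: "It is contemplated an analysis by intention to treat and the percentage of losses for each treatment group will be collected". Section 12 allows simethicone and antispasmodics, asks patients to contact the team after 72 hours without an evacuation, and says "each of the side effects will be recorded as well as the need for therapies rescues specified above" and "If there are complications will be referred directly to your treating physician".

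**The concern.** The protocol names a contraindication to one of its own study products but does not carry it into the eligibility rules. Those rules are what a site applies, and as written they admit a patient for whom the protocol itself regards one of the four treatments as unsuitable.

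The masked supply makes the entry check more important. A patient who knows that psyllium has caused a reaction cannot tell from the container that it holds psyllium, so the history has to be taken before randomisation.

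What is at stake is the safety of an individual patient. The treatment comparison is not affected.

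**Working it through.** **Step 1: exposure.** Inputs are the group sizes in section 8. 4 × 15 = 60, which reproduces the stated total. The psyllium share is 15/60 = 0.25.

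**Step 2: set each listed contraindication against the entry rules.**

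| Contraindication in section 6 | Cover at entry (sections 8 and 9) |
|---|---|
| Obstruction, sub-occlusion | Partial: exclusion of other causes of secondary constipation; colonoscopy rules; passage of the motility capsule given at visit 2, before randomisation |
| Abdominal pain | Yes: Rome III item on the last 3 months; alarm-data exclusion for the last 6 months |
| Nausea, flatulence, distension, severe meteorism | No entry criterion. Flatulence and distension are expected on treatment and have a rescue measure in section 12 |
| Hypersensitivity | None |

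The digestive symptoms in the third row are tolerability effects, several of which the protocol expects from fiber. They are not proposed here as bars to entry. Hypersensitivity is different: it is a known history that can be asked about, and no criterion touches it.

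**Step 3: does a neighbouring rule close the gap?**

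- The 2-month exclusion asks whether the patient has recently taken a supplement. Someone who gave up psyllium a year ago because of a reaction passes it.
- The review in section 8 asks about previous use and suspension of supplements and laxatives. A good history might bring out a reaction, but the text neither asks for it nor says what follows if one is reported.
- The physical evaluation at visit 2 would not reveal a past reaction unless the patient is asked.

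**Step 4: consequence for one patient.** With equal groups, a randomised patient with known psyllium hypersensitivity receives psyllium with probability 15/60 = 1/4. If *k* such patients are randomised, *k*/4 receive it on average: 0.25 for *k* = 1, 0.5 for *k* = 2. The documents give no basis for *k*, so this goes no further.

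**Step 5: consequence for the statistics.** None. The sample-size calculation (11 per group, raised to 15 for losses) and the planned tests do not depend on this criterion.

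**The case against.** **The case for leaving the plan alone.** Psyllium is first-line treatment for this condition and is used at the dose that section 6 reports as recommended. Supplement history is already reviewed, and a complete physical evaluation precedes randomisation. For harm to occur, a patient with a known reaction must go unnoticed at both. The annexes, flow chart and consent pages are not available, and an allergy question may sit in any of them.

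This limits the weight of the point but does not answer it. The safeguard would rest on what an individual clinician happens to ask. A question in an annex would help, but it would still not be an exclusion in section 9.

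**Stronger readings that the documents do not support.**

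- *The plan has no safe way to stop treatment, and patients must continue after a reaction.* A reader might infer this from "The patient will Continue with the supplement in the same container and will be scheduled for a month later". That sentence describes the visit schedule and follows a medical evaluation; it does not direct continuation after an allergic reaction. The plan also has the adverse-effect sheet, two on-treatment evaluations, rescue measures, 72-hour contact, referral, an open-ended acute-illness criterion, and an intention-to-treat analysis with reasons for loss collected. A written trigger for intolerance judged severe would only restate clinical discretion, and suspected obstruction is already substantially addressed.
- *Half the trial is at risk because two groups take at least 10 g a day.* The remark in section 6 about reactions from 10 g concerns very sensitive people, in a discussion of inulin. Group sizes are not counts of people at risk. The same section also places signs of intolerance at intakes above 20 to 30 g and reports good tolerance at 5, 10 and 20 g of inulin fructans.
- *Stops for reactions would use up the 20% loss allowance or bias the comparison.* No text says that stopping the product means leaving the study, and no frequency is given from which such losses could be projected.

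**Conclusion.** The point holds as an omission from the eligibility criteria. The protocol lists hypersensitivity as a contraindication to psyllium, gives psyllium to 15 of 60 patients (25%), and has no selection criterion in the supplied text that excludes known hypersensitivity to a study product. It should be corrected because it concerns patient safety and the remedy is very small. It does not threaten the validity of the trial.

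The conclusion rests on three assumptions: the criteria are applied as written; allocation is equal across the four groups, as planned; and no allergy exclusion stands in the annexes, flow chart or consent pages, which could not be checked. The number of patients affected is unknown and may well be zero.

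**What to change.** Add one exclusion to section 9 b): known hypersensitivity to psyllium, agave fructans or the excipient. Have it asked in section 8 when previous fiber supplement use is reviewed. It should apply to every volunteer, since any of them may be assigned to any group. The protocol names hypersensitivity as a contraindication for psyllium only; including agave fructans and the excipient is a precaution that adds nothing to the work of asking.

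An optional addition is a sentence stating that the product stops after an allergic reaction. A broader stopping rule is not requested.

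The cost is a short amendment and one extra question at an existing review. A few volunteers may become ineligible. Sample size, randomisation and analysis stay as they are.
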